9.0 Subject Disposition

Subject disposition summary will be presented on all the screened subjects by investigator site and overall. The following information will be presented:

- Subjects who were screened
- Subjects who screen failed
- Subjects who were randomized
- Subjects who were randomized without any major protocol violations

- Subjects who took at least one dose of study drug (rovalpituzumab tesirine; topotecan)
- Subjects who completed/discontinued the study drug

In addition, a subject disposition summary will be presented for the Randomized Set by treatment arm assigned at randomization – the numbers and percentages of subjects who were randomized, and discontinued the study.

In addition, treatment disposition summary will be presented for the safety set, classifying subjects according to actual treatment received. The numbers and percentages of subjects who discontinued the study drug and primary reason for study drug discontinuation will be provided. No statistical tests will be performed.

10.0 Study Drug

10.1 Study Drug Exposure

Summary of study drug exposure will be presented on the safety set.

The following summaries will be presented by treatment group:

- The number and percentage of subjects with total number of cycles of rovalpituzumab tesirine and topotecan received,
- Descriptive summary of average dose level per cycle (mg/kg for rovalpituzumab tesirine; mg for dexamethasone; mg/m² for topotecan),

An overview of interruption and dose reduction will be presented for each of rovalpituzumab tesirine, dexamethasone, and topotecan treatments as following:

- The number and percentage of subjects who had at least one interruption of study drug (rovalpituzumab tesirine/dexamethasone/topotecan) administration, and further breakdowns by the number of interruptions and by reason,
- The number and percentage of subjects who had at least one dose reduction, and further breakdowns by the number of dose reductions and by reason.

For each cycle, the number and percentages of subjects with interruption and reason will be presented (42-day cycle for rovalpituzumab tesirine; 21-day cycle for topotecan). Similarly, the number and percentages of subjects with dose reduction and reason will be presented at each cycle.

10.2 Relative Dose Intensity (RDI) of Rovalpituzumab Tesirine

Dose intensity of rovalpituzumab tesirine will be summarized for the safety set (Arm A only).

For a subject, the total dose is defined as the sum of rovalpituzumab tesirine doses (mg/kg) administered during the study. Treatment duration of rovalpituzumab tesirine is defined as total number of weeks rovalpituzumab tesirine treated, i.e., (date of last injection – date of first injection + 42)/7, by adding the appropriate number of days to complete the last cycle.

The observed dose intensity ($DI_{observed}$), expressed in units of dose level divided by unit of treatment duration, i.e., mg/kg/week, is the ratio of the total dose (mg/kg) received to the total duration of treatment (weeks);

$$DI_{observed} = \frac{\text{Total dose (mg / kg)}}{\text{Actual total treatment duration (weeks)}}$$

The theoretical dose intensity ($DI_{protocol}$) will be expressed in the same unit as those used for the observed dose intensity;

$$DI_{protocol} = \frac{\text{Dose per cycle (mg / kg)}}{\text{Theoretical duration of one cycle (weeks)}}$$

The relative dose intensity (RDI), expressed in percentage (%), is calculated as the ratio of the observed dose intensity to the dose intensity indicated in the protocol;

$$RDI = \frac{DI_{observed}}{DI_{protocol}} \times 100 .$$

Simple continuous summary statistics for the observed dose intensity will be presented. The number and percentages of subjects will be presented for the following categories of RDI < 70%, 70% to < 90%, 90% to < 110%, 110% to < 120%, and 120% or higher.

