**Additional Two Cycles of Rovalpituzumab Tesirine (Arm A only)**

Up to two additional cycles of rovalpituzumab tesirine may be permitted, however the last dose on study must be administered no later than 04 December 2019 for subjects in Arm A who provide consent and who satisfy all of the following criteria:

- achieved clinical benefit defined as stable disease or better with two initial cycles of rovalpituzumab tesirine
- have findings indicative of disease progressing (not limited to CNS) at least 12 weeks after the second dose of rovalpituzumab tesirine
- received no other systemic anti-cancer therapy after two initial cycles of rovalpituzumab tesirine
- had no prior on-study serosal effusions (Appendix I) or edema of > Grade 2 or other non-hematological treatment-related AEs of  $\geq$  Grade 3 or potential DILI and any treatment-related AEs have resolved to Grade 1 or baseline
- have no clinically significant symptoms or signs related to disease progression and/or indicating threat to vital organs and no disease progression at critical anatomical sites necessitating urgent alternative treatment
- have no decline in performance status as compared to the last radiographic assessment at which no progressive disease was identified

Any new or progressing CNS disease of such subject must be definitively treated (radiotherapy or surgery) in order for the subject to be eligible for the two additional cycles of treatment. Subjects remaining in rovalpituzumab tesirine treatment post-progression not limited to CNS will be followed radiographically until the second event of progressive disease. CT/MRI scan must be performed within one week prior to the 4th dose of rovalpituzumab tesirine.

Subjects who do not provide consent for two additional doses of rovalpituzumab tesirine should proceed to the End of Treatment (EOT) visit before continuing on to the Survival Follow Up period.

The last radiographic assessment prior to additional doses of rovalpituzumab tesirine will be used as a new baseline for purposes of subsequent disease assessment.

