5.2 Design Diagram

This is a Phase 3, randomized, open-label, multinational, and multicenter study comparing the efficacy, safety and tolerability of rovalpituzumab tesirine versus topotecan in subjects with advanced or metastatic DLL3^{high} SCLC who have first disease progression during or following front-line platinum-based chemotherapy. DLL3^{high} is defined as $\geq 75\%$ tumor cells staining positive according to the VENTANA DLL3 (SP347) IHC Assay.

Eligible subjects will be randomized in a 2:1 ratio to receive rovalpituzumab tesirine (Arm A) or topotecan (Arm B):

[figure not shown]
- Subjects assigned to Arm A will receive 0.3 mg/kg rovalpituzumab tesirine (IV) on Day 1 of a 42-Day cycle for 2 cycles, along with 8 mg orally (PO) of dexamethasone twice daily on Day –1, Day 1, and Day 2. Regimen of Arm A will be administered for the 2 cycles planned unless earlier discontinuation is warranted due to disease progression, unacceptable toxicity or any other

reason. Up to two additional cycles of rovalpituzumab tesirine may be permitted for subjects in Arm A meeting certain criteria, as described in Section 5.3.1.1 of the study protocol.

- Arm B subjects will receive 1.5 mg/m² topotecan (IV) on Days 1 – 5 of each 21-Day cycle. Topotecan may be administered at a lower dose if required by the local label. The Arm B regimen will be administered until disease progression, unacceptable toxicity or any other reason requiring treatment discontinuation.

A schematic of the study is provided in Figure 1 Study Schema.

Figure 1. Study Schema

Empty arrowhead = Rovalpituzumab tesirine administration cycle; Dotted arrowhead = Additional Rovalpituzumab tesirine administration cycle; Filled arrowhead = Topotecan administration cycle; PTFU = post-treatment follow-up; OS = overall survival

1. Tumor material collection and testing for DLL3 status may occur at any time after initial diagnosis, including outside of the Screening window, depending on completion of the appropriate consent process.
2. Up to two additional cycles of rovalpituzumab tesirine may be permitted for subjects in Arm A meeting certain criteria, as described in Protocol Section 5.3.1.1.
3. Topotecan will be administered until disease progression, unacceptable toxicity or any other reason requiring treatment discontinuation.

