			Day -1	Day 1 ^e (-3 d)	Day 2	Day 8 (± 3 d)	Day 15 (± 3 d)	Day 22 (± 3 d)	Day 29 (± 3 d)	Day 36 (± 3 d)		q6/q9 Weeks (± 1 wk)	q6 Weeks (± 1 wk)		q9 Weeks (± 1 wk)
PK and PD/ Biomarker	Pharmacokinetics, Anti-therapeutic Antibody (ATA) and Neutralizing Antibodies (nAb) ^w		X								X				
	Archived or Fresh Tumor Material ^x	X													
	Tumor Material at Time of Disease Progression ^y										X		X		
	Blood for Inflammatory Markers and ctDNA (10 mL) ^z		X								X ^z		X ^z		
	Blood for Tumor & Soluble Markers (5 mL) ^z		X								X ^z		X ^z		
	Circulating Tumor Cells (10 mL) ^{aa}	X	X								X				
	Pharmacogenetics (DNA/RNA) ^{bb}		X ^{bb}								X				
	Serosal Fluid ^{cc}														
					Day 1 through 70 days after last study treatment										

-
- a. Up to two additional cycles of rovalpituzumab tesirine may be permitted for subjects in Arm A meeting criteria as described in Protocol Section 5.3.1.1. Subjects receiving additional doses of rovalpituzumab tesirine will follow the same study schedule as in Cycles 1 and 2.
 - b. EOT Visit occurs within 7 days of documentation of the decision to discontinue treatment and prior to subjects beginning any new anti-cancer therapy if possible. Subjects in Arm A should be evaluated for eligibility of two additional doses of rovalpituzumab tesirine prior to proceeding with EOT procedures.
 - c. For subjects who discontinue investigational product for reasons other than disease progression, the first PTFU visit will occur at 6 weeks (\pm 1 week) after the last Disease/Response Assessment, then every 6 weeks (\pm 1 week) until disease progression or initiation of new anti-cancer therapy, whichever occurs first.
 - d. Subjects will be followed for subsequent anti-cancer therapies (dates and responses), as well as survival status, every 6 weeks* (\pm 1 week) until the endpoint of death, the subject becomes lost to follow-up or withdraws consent, or termination of the study by AbbVie, whichever occurs first (* or as requested by AbbVie to support data analysis).

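### The relative dose intensity formula counts the protocol-required gap before retreatment as treatment time, which caps a fully dosed, on-schedule retreated subject at 75% (three doses) or 80% (four doses)

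*SAP*

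**What the plan says.** SAP 10.2 builds RDI for Arm A, in the safety set, from three pieces.

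- Total dose is "the sum of rovalpituzumab tesirine doses (mg/kg) administered during the study", so doses given at retreatment are included.
- Treatment duration in weeks is "date of last injection – date of first injection + 42)/7" (the bracket opens just before the quoted words). The 42 days are justified as "by adding the appropriate number of days to complete the last cycle". Nothing in the section removes off-treatment time or mentions retreatment.
- The reference intensity is the dose per cycle divided by the theoretical length of one cycle. SAP 5.2 gives the regimen as "0.3 mg/kg rovalpituzumab tesirine (IV) on Day 1 of a 42-Day cycle for 2 cycles".

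Observed dose intensity is total dose over duration, and RDI is that figure as a percentage of the reference. The SAP plans summary statistics for observed dose intensity and a count of subjects in five RDI categories: below 70%, 70% to below 90%, 90% to below 110%, 110% to below 120%, and 120% or more.

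On retreatment, Protocol 5.3.1.1 says "Up to two additional cycles of rovalpituzumab tesirine may be permitted". Among the conditions, the subject must "have findings indicative of disease progressing (not limited to CNS) at least 12 weeks after the second dose of rovalpituzumab tesirine". SAP Appendix A, footnote a, adds: "Subjects receiving additional doses of rovalpituzumab tesirine will follow the same study schedule as in Cycles 1 and 2".

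**The concern.** For retreated subjects the two sides of the ratio do not describe the same thing. Observed intensity runs over the whole span from first to last injection, including a gap without which the subject could not have been retreated. The reference intensity assumes an unbroken run of 6-week cycles. A subject who received every dose in full and on schedule therefore cannot score near 100%.

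What is at stake is how one descriptive exposure summary reads. Retreated, fully dosed subjects have the highest total dose in Arm A (0.9 or 1.2 mg/kg, against 0.6 mg/kg for two cycles), yet they would sit in the lower RDI categories. Protocol 5.6.4 reports that delayed or cumulative toxicity in the Phase 1 study seemed to track total dose, so a reader may well look at this table beside the safety results.

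**Working it through.** **Inputs**

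- Dose and cycle: 0.3 mg/kg every 42 days (SAP 5.2), so the reference intensity is 0.3/6 = 0.05 mg/kg/week.
- Duration and total dose: SAP 10.2, as above.
- Number of doses: two initially, three or four with retreatment (Protocol 5.3.1.1).
- Shortest interval from dose 2 to dose 3: 12 weeks, or 84 days (Protocol 5.3.1.1).
- Spacing of dose 3 to dose 4: 42 days (SAP Appendix A, footnote a).
- No dose above 0.3 mg/kg (Protocol 5.6.4), so a larger dose cannot offset the gap.

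**Formula.** For n full doses and T = last − first + 42 days,

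RDI = 100 × [0.3n/(T/7)]/0.05 = 100 × 42n/T.

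The SAP states no RDI value to reproduce. The formula does behave as intended in the initial course: one dose gives T = 42 and two doses 42 days apart give T = 84, and both give 100%.

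**Retreated subjects.** Let g be the days from dose 2 to dose 3.

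- Three doses: T = 42 + g + 42 = 84 + g, so RDI = 12600/(84 + g).
- Four doses: T = 42 + g + 42 + 42 = 126 + g, so RDI = 16800/(126 + g).

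| Gap g | 3 doses (0.9 mg/kg) | 4 doses (1.2 mg/kg) |
|---|---|---|
| 84 days (12 weeks, protocol minimum) | 24 weeks, 75.0% | 30 weeks, 80.0% |
| 112 days (16 weeks, illustrative) | 28 weeks, 64.3% | 34 weeks, 70.6% |
| 126 days (18 weeks, illustrative) | 30 weeks, 60.0% | 36 weeks, 66.7% |
| 168 days (24 weeks, illustrative) | 36 weeks, 50.0% | 42 weeks, 57.1% |

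**Category limits**

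- RDI falls below 70% when g exceeds 12600/70 − 84 = 96 days (three doses) or 16800/70 − 126 = 114 days (four doses).
- Reaching 90% would need g of at most 12600/90 − 84 = 56 days or 16800/90 − 126 = 60.7 days. Both are under the 84-day minimum.

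**Sensitivity to visit windows.** If doses 2 and 4 are each given 3 days early, T is 165 or 204 days, and RDI is 12600/165 = 76.4% or 16800/204 = 82.4%. The category does not change.

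**What the table cannot separate.** All three of these subjects fall in the 70% to below 90% category:

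- a three-dose retreated subject, fully dosed with the shortest gap: 75.0%;
- a two-dose subject whose second dose is 28 days late: T = 70 + 42 = 112 days, RDI = 8400/112 = 75.0%;
- a two-dose subject, on time, reduced to 0.2 mg/kg at dose 2 (a level in Protocol Table 5): 0.5 mg/kg over 12 weeks, RDI = (0.5/12)/0.05 = 83.3%.

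**With durations summed by course.** The initial course is 42 + 42 = 84 days (12 weeks). The additional course is 42 days (6 weeks) for one dose or 84 days (12 weeks) for two. RDI is (0.9/18)/0.05 = 100% or (1.2/24)/0.05 = 100%, whatever the gap.

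**The case against.** Dose per elapsed week from first to last injection is a coherent quantity, and SAP 10.2 defines it explicitly. A reader might infer that 100% is the only correct value for these subjects. The documents do not support that: 100% is the value under a by-course convention. What stands is narrower. The reference intensity leaves out a gap that the observed intensity includes, so their ratio misleads for retreated subjects. The words before the formula, which describe weeks treated, could be taken to mean on-treatment time only, but the formula that follows settles the calculation and counts the gap.

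SAP 10.1 gives partial cover. It reports the number of cycles, the average dose per cycle, and interruptions and reductions with reasons. A fully dosed retreated subject would appear there with three or four cycles at full dose. It would therefore be wrong to say that the exposure reporting as a whole shows under-dosing. These tables do not correct the RDI summary, however, and no split by retreatment is planned.

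A reader might also infer that exposure-response or safety conclusions are distorted. Protocol 8.1.7 bases exposure-response on pharmacokinetics and reports it separately, and no analysis in SAP 12 is stratified by or adjusted for RDI.

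Finally, the retreated group may be small, since the eligibility conditions are demanding. Protocol 3.3 cites progression-free survival of 3.9 months (3.9 × 30.4375/7 = about 17 weeks) in third-line patients. If that were a median and carried over to this population, which is an assumption, more than half would progress or die before the qualifying time of about 18 weeks after dose 1. This limits the effect on the table as a whole but not the error for each subject affected.

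**Conclusion.** The point holds as a defect of definition in SAP 10.2. No stated figure is miscalculated, and the 42-day term is not at fault; the problem is the uninterrupted span from first to last injection. For full doses at exact 42-day spacing within each course, RDI is at most 75% with three doses and 80% with four, and about 76% and 82% if doses 2 and 4 are 3 days early. The 90% to below 110% category is out of reach, and gaps beyond 96 or 114 days put the subject below 70%. Only the 12-week minimum comes from the documents; the longer gaps are illustrations.

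The consequence is limited to the descriptive Arm A summaries of observed dose intensity and RDI, and to retreated subjects, whose number the documents do not give. No efficacy or error-rate result depends on it. It is a minor point but worth correcting.

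**What to change.** In SAP 10.2, calculate observed dose intensity and RDI separately for the initial course (cycles 1–2) and the additional course (cycles 3–4). If a combined value is also shown, divide total dose by the sum of the two course durations, each taken as last minus first injection within the course plus 42 days.

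The cost is a sentence or two in the SAP and a small programming change, using the same doses and injection dates as the present formula. SAP 4.0 describes the plan as a draft still to be finalized, so the change can go in before comparative analysis. No dosing or retreatment rule is touched.

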11.0 Efficacy Analysis

11.1 General Considerations

Unless otherwise specified, all efficacy analyses described below will be performed on the Randomized Set. Efficacy endpoints of response and progression used in analyses will be based on Central Radiographic Assessment Committee (CRAC). Disease progression will be defined as progression of disease according to RECIST v1.1. For subjects whose tumors meet the criteria of partial or complete response (PR or CR), tumor response must be confirmed by repeat measurements performed no less than 4 and no more than 8 weeks after the criteria for response are first met.

For change from baseline analysis of QOL measures, patients with missing baseline value will be excluded. Descriptive summaries for the efficacy endpoints will be reported by treatment groups. These summaries will also be reported at the individual levels of each stratification factors.

The statistical comparisons for the primary and secondary endpoints will be done according to the multiplicity adjustment plan described in Section 5.7.2 to preserve the familywise one-sided type 1 error rate to 0.025. The statistical comparisons for all the other exploratory efficacy endpoints will be performed at a nominal one-sided 2.5% significance level. Confidence intervals for parameters (e.g., median survival times, HR) will be constructed with 2-sided 95% confidence level, whenever applicable. No type I error adjustment for multiple comparisons will be carried out for these exploratory endpoints.

11.1.1 Analysis of Efficacy Endpoints by Variable Type

Time to events (TTE) variables

All TTE endpoints defined in this study are concerned with only the first incidence of an event of interest, and recurrence of the same event is not considered for endpoint derivation. An event however may be defined in a composite manner, i.e., as the occurrence of one among several different outcomes. The composite event is observed when at least one of the component events occurs, and the time to the earliest among the occurring component events is considered to be the TTE for the composite event.

Time to events (TTE) endpoints will be derived as follows:

$$\text{TTE} = \text{Date of first occurrence of an event or censoring} - \text{date of randomization} + 1.$$

TTE endpoints will be computed in days and converted into months (1 month = 30.4375 days) for analysis. Thus, for subjects who experience the event of interest, time to event will be defined as the time from randomization to the first occurrence of the event. When multiple assessments are needed to ascertain the occurrence of an event, the earliest date among all of these assessments is taken to be date of the event or censoring. For a subject who does not experience an event on the study, time will be right censored at the time of his/her last available adequate post-baseline assessment that rules out the occurrence of the event. If a subject had no post-baseline assessment and did not experience the event of interest, then TTE will be censored at the date of randomization and we will set $\text{TTE} = 1$ day, by convention.

TTE endpoints will be summarized by number of events observed, number of subjects censored, and times corresponding to 25% (1st quartile), 50% (median) and 75% (3rd quartile) event probabilities. Kaplan-Meier (KM) estimates will be calculated and plotted. Comparison between treatment arms will be based on stratified log-rank tests as specified.

A Cox proportional-hazards regression model⁴ with the treatment and stratification factors as covariates will be used to estimate the HR of rovalpituzumab tesirine to topotecan and its two-sided 95% CI. Only the main effects of the stratification variables will be fitted. Measure of treatment effects will be provided in term of HR (rovalpituzumab tesirine to Topotecan) from the above model with HR value less than 1 representing treatment benefit. For all of the above time-to-deterioration endpoints, death will be considered as event.

Continuous variables

Summary of continuous endpoints at baseline, post-baseline and change from baseline (as available) will be provided. Change from baseline values will be analyzed using an analysis of covariance (ANCOVA) model including stratification factors and baseline as covariates and 95% CI for treatment group difference will be provided.

11.2 Efficacy Analyses

Overall Survival (OS)

All events of death available at the time of analysis will be included, regardless of whether the event occurred while the subject was still taking study drug or after the subject discontinued study drug.

The primary endpoint OS will be compared between treatment Arms rovalpituzumab tesirine and topotecan at both interim and final analysis. Superiority of rovalpituzumab tesirine (Arm A) to topotecan (Arm B) in terms of OS will be evaluated using stratified log-rank test, adjusting for the study stratification factors.

This stratified log rank test will be implemented in SAS using LIFETEST procedure as follows:

```
proc lifetest method=km;  
  time <follow-up time>*<Censoring status>(<censoring codes>);  
  strata <stratification factors> / group=<treatment>  
      test = logrank;  
run;
```

The OS curves for each arm will be estimated using the Kaplan-Meier (KM) product-limit method. Two-sided, 95% confidence interval for median OS will be computed, using the Brookmeyer and Crowley method. Landmark survival rate, defined as the survival rate estimated using the Kaplan-Meier approach at pre-defined time points from randomization (e.g., 6, 12, 18, and 24 months), will be presented with two-sided 95% CIs, using Greenwood's method for calculating standard errors.

Estimation of HR

A Cox proportional-hazards regression model⁴ with the treatment and stratification factors as covariates will be used to estimate the HR of rovalpituzumab tesirine to topotecan and its two-sided 95% CI. Only the main effects of the stratification variables will be fitted.

Where, treatment takes value 1, if treated with rovalpituzumab tesirine, otherwise 0, for topotecan. Efron's approximate method (1977) will be used for handling ties. In SAS, estimate of HR will be estimated using PHREG procedure and Efron's method⁵ will be employed by using TIES = EFFRON option in MODEL statement.¹⁹ Following SAS code will be used

```
PROC PHREG;  
  CLASS <treatment>;  
  MODEL <follow-up time>*<Censoring status>(<censoring codes>)=  
<strata variables> <treatment> /TIES=EFFRON RL;  
RUN;
```

Progression-free Survival (PFS)

All disease progression assessed by CRAC per RECIST v1.1 will be included, regardless of whether the event occurred while subject was taking the study drug or had previously

discontinued the study drug. Data from subjects who are lost to follow-up will be included in the analysis as censored observations on the last date of radiographic assessment that the subject was documented to be progression free.

Analysis methods for PFS endpoint are similar to those described for the OS endpoint. The PFS rates at 6, 9 and 12 months and corresponding 95% CIs will also be estimated using KM estimates on the PFS curve for each arm.

Clinical Benefit Rate (CBR)

Subjects with clinical benefit includes those who achieve confirmed complete or partial response (CR or PR), or stable disease (SD) for at least 12 weeks (2 tumor assessments) as adjudged by the CRAC based on RECIST v1.1.

The clinical benefit rate (CR, PR, and SD) rate will be reported with exact (binomial) two-sided 95% CI for each treatment arm.

CBR will be compared between treatment arms using a Cochran-Mantel-Haenszel (CMH) test, stratified by the randomization stratification factors. The difference in CBR will be summarized with two-sided 95% CI. Rates and corresponding 95% exact CIs will be calculated by Clopper-Pearson method for each arm. Sensitivity analysis based on investigator-determined CBR will also be performed.

Objective Response Rate (ORR)

Analysis of ORR will be performed for the randomized subjects with measureable disease at baseline.

Objective response includes complete response (CR) and partial response (PR) assessed by the CRAC based on RECIST v1.1. Subjects who do not achieve CR or PR, including those who do not have post-baseline radiological assessments will be considered as non-responders.

The same statistical methodology will be used as that for CBR endpoint.

Duration of Response (DOR)

Only subjects with a confirmed objective response will be included in the analysis of duration of response (DOR).

DOR is defined as the time between the date of first response (CR or PR by CRAC, whichever is recorded first) to the date of the first documented tumor progression (assessed by CRAC) or death due to any cause, whichever comes first. If a subject is still responding (i.e., has not progressed nor died after CR or PR), then the subject's data will be censored at date of the last radiographic assessment by CRAC. For subjects who never experienced CR or PR, these subjects' data will not be included in the duration of response analysis.

Distribution of the duration of response will be estimated for each treatment arm using Kaplan-Meier methodology. Median duration of overall response with corresponding 95% CI for each treatment arm will be provided. Due to the non-randomization nature of the analysis set for DOR, the analysis of DOR will be considered descriptive and will not be compared between treatment arms.

Patients Reported Outcomes (PRO)

The endpoints based on subject self-reported health related quality of life (QoL) and symptom assessments will be analyzed for post-treatment Week 3, Week 7 and subsequently with the increment of 6 weeks (i.e., Week 13, Week 19, and Week 24). The EORTC QLQ-C15-PAL/LC13 and the European Quality of Life-5 Dimensions (EQ-5D-5L) are used to measure the QoL and symptom assessments.

QLQ-C15-PAL & QLQ-LC13

The QLQ-C15-PAL is an abbreviated 15-item version of the EORTC QLQ-C30 for palliative care. The QLQ-C15-PAL questionnaire has four abbreviated scales measuring physical functioning, emotional functioning, nausea and vomiting, and fatigue. These

scales are estimated using the algorithm specified in *Addendum to the EORTC QLQ-C30 Scoring Manual: Scoring of the EORTC QLQ-C15-PAL* (July, 2006).

For each scale in QLQ-C15-PAL questionnaire, the raw score (RS) is computed as the mean of component items over the number of items answered for that scale if at least 50% of the items are answered, and set as missing otherwise. Then the scale score (SS) will be computed as:

$$SS = \{(RS - 1)/range\} \cdot 100.$$

The lung cancer module (QLQ-LC13) is composed of one multi-item scale to assess dyspnea, and a series of single items assessing coughing, sore mouth, dysphagia, peripheral neuropathy, alopecia, hemoptysis, and pain.

All scales and single items are reported on categorical responses, and will be linearly converted to 0 through 100 numeric values. Given a scale, the raw score (RS) is computed as the mean of component items over the number of items answered for that scale if at least 50% of the items are answered. It will be set as missing otherwise. Then the scale score, $SS = \{(RS - 1)/range\} \cdot 100$, will be computed.

For single-item measures (dyspnea, insomnia, appetite loss, constipation, diarrhea, and financial difficulties), none of the single-item measures can be computed if not answered. If a scale score cannot be computed, the outcome for that score is left blank.

The analysis of continuous endpoint of EORTC QLQ-C15-PAL PF scale score will be performed by analyzing the change in scale score from baseline to the given time point, using an analysis of covariance (ANCOVA) model including stratification factors and baseline as covariates, and 95% CI for treatment group difference will be provided.

Change from baseline at post-baseline Week 7 in the physical function scale is one of the secondary efficacy endpoints, and other scales and items are considered exploratory.

For each scale, the treatment group differences will be evaluated by analyzing the change from baseline to each of the post-baseline time-points and to the final measurement (last QoL assessment per subject) using a one-way analysis of variance (ANOVA) model including stratification factors and baseline as covariates. Simple summary statistics for QoL assessments at each timepoint will also be presented.

EQ-5D-5L

The EuroQol 5 Dimensions 5 Level (EQ-5D-5L) is a preference based measure of health status that consists of EQ-5D descriptive system and EQ visual analogue scale (VAS).

The EQ-5D descriptive system comprises the following 5 dimensions: mobility, self-care, usual activities, pain/discomfort, and anxiety/depression. Each of the dimensions is divided into 5 levels of perceived problems: Level 1 (indicating no problem), Level 2 (indicating slight problems), Level 3 (indicating moderate problems), Level 4 (indicating severe problems), and Level 5 (indicating extreme problems). EQ-5D-5L health status, defined by the EQ-5D-5L descriptive system, will be converted into a single preference –weighted health status or "utility" index score by applying country-specific weights (if available) or U.S. weights (if not available).

The EQ VAS records the respondent's self-rated health on a visual analogue scale (0 to 100). The VAS score will be measured separately.

Mean change from baseline in EQ-5D-5L "utility" index score to each applicable post-baseline time point, and to the final measurement will be presented by treatment arm. The treatment group difference will be evaluated by analyzing the change from baseline using a one-way analysis of variance (ANOVA) model including stratification factors and baseline as covariates. The same methodology will apply to the mean change from baseline in VAS score.

